### 3.2 Efficacy Analyses

Summarization and analysis of efficacy parameters will be conducted for the ITT population (primary analysis) and PP population (secondary confirmatory analysis) by treatment group.

### 3.2.2 Secondary Variables

#### 3.2.2.1 Area Under the Curve for C-peptide During First 4 Hours of a Mixed Meal Tolerance Test

C-peptide is to be collected at 9 time points (2 basal measurements and at 15, 30, 60, 90, 120, 180, and 240 minutes) during the first 4 hours of a mixed meal tolerance test on both Days 75 and 365 after IAT. For both Days 75 and 365, the AUC will be computed as described in Section 2. AUC values at each day will be summarized descriptively by treatment group, and analyzed as described in section 7.5.2.1 of the SAP version 2.0.

Change (absolute and percentage) in AUC values from Day 75 to Day 365 ( $\Delta_{75-365}$ ) will be summarized descriptively by treatment group, and analyzed using a t-test to compare treatment groups (two-sided tests at the 5% level of significance) and using a general linear model which includes change in AUC as the response; treatment group and study site as fixed main effects; and the treatment by study site interaction if significant at the 0.10  $\alpha$ -level. Least squares means, standard errors, and associated 95% confidence intervals will be presented for each treatment group, along with the least square mean difference (reparixin minus placebo), standard error, associated 95% confidence interval, and p-value (two sided at the 5% level of significance). Data transformations will be considered, if appropriate.

Data will be plotted as a regression curve for  $AUC_{0-240}$  versus IEQ/kg on days 75 and 365 after IAT by treatment group. The slope and intercept of the regression line and  $R^2$  will be calculated and displayed on the figure. The p-value testing the slope for difference from zero will also be displayed. In addition, regression curve  $AUC_{0-240}$  versus IEQ/kg will be plotted and analyzed only for patients receiving IEQ/kg  $\leq 5000$ .

#### 3.2.2.2 Average Daily Insulin Requirements

The average daily insulin requirement (ADIR) will be computed by site personnel using data from either the patient diary card or other appropriate source documents/information and reported on Pages 24 and 24.1 for Days 75 and 365, respectively.

In addition to the analyses described in Section 7.5.2.2 of SAP version 2.0, ADIR at Day 75 and Day 365 will be analyzed as repeated measures with a single repeated measurements model, as specified in the SAP, but also including IEQ/kg infused at IAT (<2500 IEQ/kg, 2500-5000 IEQ/kg, and >5000 IEQ/kg) as a fixed effect term. The importance of the treatment-by-IEQ/kg infused at IAT interaction will be investigated and if the term is not significant at the 0.10  $\alpha$ -level, it will be excluded from the model. If the addition of the IEQ/kg infused at IAT factors into the model cause the data to be too sparse for the model to converge, the repeated measures analysis will not be performed.

Summary statistics for ADIR at Day 75 and Day 365 will be provided for each IEQ/kg infused at IAT category (<2500 IEQ/kg, 2500-5000 IEQ/kg, and >5000 IEQ/kg) and treatment group. ADIR at Day 75 and Day 365 will be compared across treatment groups within each IEQ/kg infused at IAT category using a t-test.

#### 3.2.2.3 Proportion of Patients With HbA1c $\leq 6.5\%$ at Day 365

The percentage of patients with HbA1c  $\leq 6.5\%$  at Day 365  $\pm 14$  days after IAT, as specified in Section 7.5.2.5 of SAP version 2.0, will also be compared between treatment groups using the Cochran-Mantel-Haenszel test stratified by baseline IEQ/kg (<2500 IEQ/kg, 2500-5000 IEQ/kg, and >5000 IEQ/kg). The hypothesis to be tested is:

Null Hypothesis,  $H_0$ :  $p_{\text{reparixin}} \leq p_{\text{placebo}}$  for all baseline IEQ/kg strata

Alternative Hypothesis,  $H_A$ :  $p_{\text{reparixin}} > p_{\text{placebo}}$  for at least one baseline IEQ/kg strata

REP0112

Addendum to Statistical Analysis Plan

The significance level used for statistical testing will be 2.5% and a one-sided test will be used. The 95% confidence interval for treatment proportions and the one-sided 95% confidence interval for the difference in treatment proportion between reparixin and placebo will be produced.

#### 3.2.2.4 Proportion of Patients With HbA1c $\leq$ 7% at Day 365 and Free of Severe Hypoglycemic Events From Day 75 Through Day 365

The same analyses described in Section 7.5.2.7 of SAP version 2.0 will be used to analyze the proportion of patients with HbA1c  $\leq$  7% at Day 365 and free of severe hypoglycemic events from Day 75 through Day 365.

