Page will be repeated for Percent Change in AUC (Day 365 – Day 75)

Reference: 16.2.6.3.2

Note: AUC = Area Under the Curve, LS = Least Squares, SE = Standard Error, CI = Confidence Interval. Least squares means, standard errors, and confidence intervals come from a general linear model which includes change in AUC as the response; treatment group and study site as fixed main effects; and the treatment by study site interaction if significant at the 0.10  $\alpha$ -level.

Dompé farmaceutici S.p.A  
Protocol REP0112

Page X of Y

Table 14.2.3.3.1 Change in Area Under the Curve for C-peptide (Alternate Computation) During First 4 Hours of a Mixed Meal Tolerance Test – Intent to Treat Population

Table 14.2.3.3.2 Change in Area Under the Curve for C-peptide (Alternate Computation) During First 4 Hours of a Mixed Meal Tolerance Test – Per Protocol Population

Table 14.2.4.X Average Daily Insulin Requirements, Stratified by IEQ/kg – [Analysis Population]

	Reparixin (N = XX)	Placebo (N = XX)
Average Daily Insulin Requirement at Day 75 (IU/kg/day)		
<2500 IEQ/kg Infused at IAT		
N	XX	XX
Mean	X.XXX	X.XXX
SD	X.XXXX	X.XXXX
Median	X.XXX	X.XXX
Min	X.XX	X.XX
Max	X.XX	X.XX
p-value Comparing Treatments Using t-test	0.XXX	
LS Mean (SE)	X.XXX (X.XXXX)	X.XXX (X.XXXX)
95% CI for LS Mean	(X.XXX, X.XXX)	(X.XXX, X.XXX)
LS Mean Difference, Reparixin – Placebo (SE)	X.XXX (X.XXXX)	
95% CI for LS Mean Difference	(X.XXX, X.XXX)	
p-value	0.XXX	
2500-5000 IEQ/kg Infused at IAT		
N	XX	XX
Mean	X.XXX	X.XXX
SD	X.XXXX	X.XXXX
Median	X.XXX	X.XXX
Min	X.XX	X.XX
Max	X.XX	X.XX
p-value Comparing Treatments Using t-test	0.XXX	
LS Mean (SE)	X.XXX (X.XXXX)	X.XXX (X.XXXX)
95% CI for LS Mean	(X.XXX, X.XXX)	(X.XXX, X.XXX)
LS Mean Difference, Reparixin – Placebo (SE)	X.XXX (X.XXXX)	
95% CI for LS Mean Difference	(X.XXX, X.XXX)	
p-value	0.XXX	

Dompé farmaceutici S.p.A  
Protocol REP0112

Page X of Y

>5000 IEQ/kg Infused at IAT		
N	XX	XX
Mean	X.XXX	X.XXX
SD	X.XXXX	X.XXXX
Median	X.XXX	X.XXX
Min	X.XX	X.XX
Max	X.XX	X.XX
p-value Comparing Treatments Using t-test	0.XXX	
LS Mean (SE)	X.XXX (X.XXXX)	X.XXX (X.XXXX)
95% CI for LS Mean	(X.XXX, X.XXX)	(X.XXX, X.XXX)
LS Mean Difference, Reparixin – Placebo (SE)	X.XXX (X.XXXX)	
95% CI for LS Mean Difference	(X.XXX, X.XXX)	
p-value	0.XXX	
Overall		
N	XX	XX
Mean	X.XXX	X.XXX
SD	X.XXXX	X.XXXX
Median	X.XXX	X.XXX
Min	X.XX	X.XX
Max	X.XX	X.XX
p-value Comparing Treatments Using t-test	0.XXX	
LS Mean (SE)	X.XXX (X.XXXX)	X.XXX (X.XXXX)

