95% CI for LS Mean	(X.XXX, X.XXX)	(X.XXX, X.XXX)
LS Mean Difference, Reparixin – Placebo (SE)	X.XXX (X.XXXX)	
95% CI for LS Mean Difference	(X.XXX, X.XXX)	
p-value	0.XXX	

Reference: 16.2.6.1, 16.2.6.4

Note: LS = Least Squares, SE = Standard Error, CI = Confidence Interval. Least squares means, standard errors, and confidence intervals come from a mixed repeated measures model which includes average daily insulin requirement (IU/kg/day) as the response; treatment group, time, IEQ/kg infused at IAT, and study site as fixed main effects; the treatment by time interaction; the treatment by study site interaction and treatment by IEQ/kg infused at IAT interaction if significant at the 0.10  $\alpha$ -level; patient as a random effect; and uses a [to be specified] covariance structure.

Dompé farmaceutici S.p.A  
Protocol REP0112

Page X of Y

Table 14.2.4.X Average Daily Insulin Requirements, Stratified by IEQ/kg – [Analysis Population]

	Reparixin (N = XX)	Placebo (N = XX)
Average Daily Insulin Requirement at Day 365 (IU/kg/day)		
<2500 IEQ/kg Infused at IAT		
N	XX	XX
Mean	X.XXX	X.XXX
SD	X.XXXX	X.XXXX
Median	X.XXX	X.XXX
Min	X.XX	X.XX
Max	X.XX	X.XX
p-value Comparing Treatments Using t-test	0.XXX	
LS Mean (SE)	X.XXX (X.XXXX)	X.XXX (X.XXXX)
95% CI for LS Mean	(X.XXX, X.XXX)	(X.XXX, X.XXX)
LS Mean Difference, Reparixin – Placebo (SE)	X.XXX (X.XXXX)	
95% CI for LS Mean Difference	(X.XXX, X.XXX)	
p-value	0.XXX	
2500-5000 IEQ/kg Infused at IAT		
N	XX	XX
Mean	X.XXX	X.XXX
SD	X.XXXX	X.XXXX
Median	X.XXX	X.XXX
Min	X.XX	X.XX
Max	X.XX	X.XX
p-value Comparing Treatments Using t-test	0.XXX	
LS Mean (SE)	X.XXX (X.XXXX)	X.XXX (X.XXXX)
95% CI for LS Mean	(X.XXX, X.XXX)	(X.XXX, X.XXX)
LS Mean Difference, Reparixin – Placebo (SE)	X.XXX (X.XXXX)	
95% CI for LS Mean Difference	(X.XXX, X.XXX)	
p-value	0.XXX	

Dompé farmaceutici S.p.A  
Protocol REP0112

Page X of Y

>5000 IEQ/kg Infused at IAT		
N	XX	XX
Mean	X.XXX	X.XXX
SD	X.XXXX	X.XXXX
Median	X.XXX	X.XXX
Min	X.XX	X.XX
Max	X.XX	X.XX
p-value Comparing Treatments Using t-test	0.XXX	
LS Mean (SE)	X.XXX (X.XXXX)	X.XXX (X.XXXX)
95% CI for LS Mean	(X.XXX, X.XXX)	(X.XXX, X.XXX)
LS Mean Difference, Reparixin – Placebo (SE)	X.XXX (X.XXXX)	
95% CI for LS Mean Difference	(X.XXX, X.XXX)	
p-value	0.XXX	
Overall		
N	XX	XX
Mean	X.XXX	X.XXX
SD	X.XXXX	X.XXXX
Median	X.XXX	X.XXX
Min	X.XX	X.XX
Max	X.XX	X.XX
p-value Comparing Treatments Using t-test	0.XXX	
LS Mean (SE)	X.XXX (X.XXXX)	X.XXX (X.XXXX)
95% CI for LS Mean	(X.XXX, X.XXX)	(X.XXX, X.XXX)

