LS Mean Difference, Reparixin – Placebo (SE)	X.XXX (X.XXXX)	
95% CI for LS Mean Difference	(X.XXX, X.XXX)	
p-value	0.XXX	
Final Model p-values		
Treatment	0.XXX	
Time	0.XXX	
Study Site	0.XXX	
IEQ/kg Infused at IAT	0.XXX	
Treatment by Time Interaction	0.XXX	

Dompé farmaceutici S.p.A  
Protocol REP0112

Page X of Y

Treatment by Study Site Interaction [only included in final model and displayed if significant at the 0.10 $\alpha$ -level]	0.XXX
Treatment by IEQ/kg Infused at IAT Interaction [only included in final model and displayed if significant at the 0.10 $\alpha$ -level]	0.XXX

---

Reference: 16.2.6.1, 16.2.6.4

Note: LS = Least Squares, SE = Standard Error, CI = Confidence Interval. Least squares means, standard errors, and confidence intervals come from a mixed repeated measures model which includes average daily insulin requirement (IU/kg/day) as the response; treatment group, time, IEQ/kg infused at IAT, and study site as fixed main effects; the treatment by time interaction; the treatment by study site interaction and treatment by IEQ/kg infused at IAT interaction if significant at the 0.10  $\alpha$ -level; patient as a random effect; and uses a [to be specified] covariance structure.

The following tables will be created from the above shell:

Table 14.2.4.1.1 Average Daily Insulin Requirements, Stratified by IEQ/kg – Intent to Treat Population

Table 14.2.4.2.1 Average Daily Insulin Requirements, Stratified by IEQ/kg – Per Protocol Population

Dompé farmaceutici S.p.A  
Protocol REP0112

Page X of Y

Table 14.2.14.X Proportion of Patients With HbA1c ≤6.5% at Day 365, Stratified by IEQ/kg – [Analysis Population]

	Reparixin (N = XX)			Placebo (N = XX)			p-value	Reparixin Minus Placebo	
	n	%	95% CI	n	%	95% CI		Estimate	95% CI
HbA1c ≤6.5% at Day 365 [n (%)]									
Overall	XX	XXX.X	(XXX.X, XXX.X)	XX	XXX.X	(XXX.X, XXX.X)	0.XXX	XXX.X	(XXX.X, -)
<2500 IEQ/kg Infused at IAT	XX	XXX.X	(XXX.X, XXX.X)	XX	XXX.X	(XXX.X, XXX.X)			
2500-5000 IEQ/kg Infused at IAT	XX	XXX.X	(XXX.X, XXX.X)	XX	XXX.X	(XXX.X, XXX.X)			
>5000 IEQ/kg Infused at IAT	XX	XXX.X	(XXX.X, XXX.X)	XX	XXX.X	(XXX.X, XXX.X)			

Reference: 16.2.6.2

Notes: p-value comparing proportion of patients with HbA1c ≤6.5% at Day 365 between treatment groups using a Cochran-Mantel-Haenszel test controlling for IEQ/kg at baseline.

The following tables will be created using the above shell:

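### When treatment-by-IEQ/kg is dropped, the addendum's stratified insulin table prints one pooled difference, CI and p-value in every IEQ/kg stratum

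*SAP*

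**What the plan says.** Addendum 3.2.2.2 analyses average daily insulin requirement at Day 75 and Day 365 "with a single repeated measurements model", with the three IEQ/kg categories added as a fixed effect. The interaction is conditional on a test at the 0.10 level: "The importance of the treatment-by-IEQ/kg infused at IAT interaction will be investigated and if the term is not significant at the 0.10". The stated consequence for a term that fails this test is "it will be excluded from the model". The same section separately asks for summary statistics and a t-test within each IEQ/kg category at each visit.

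The table shell is headed "Average Daily Insulin Requirements, Stratified by IEQ/kg" (Tables 14.2.4.1.1 and 14.2.4.2.1). At each visit it has four blocks: <2500, 2500-5000, >5000 IEQ/kg and Overall. Each block carries descriptive statistics, a t-test p-value, a least squares mean per arm, and then "LS Mean Difference, Reparixin – Placebo (SE"), its 95% CI and a p-value.

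The footnote gives one source for the model-based rows: "Least squares means, standard errors, and confidence intervals come from a mixed repeated measures model which includes average daily insulin requirement (IU/kg/day) as the response". Always in that model are treatment, time, IEQ/kg, site and treatment-by-time. Added to them are "the treatment by study site interaction and treatment by IEQ/kg infused at IAT interaction if significant at the 0.10" level. The final-model block repeats the condition: "Treatment by IEQ/kg Infused at IAT Interaction [only included in final model and displayed if significant". The text available does not say what the stratum rows should contain when the term is absent.

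**The concern.** A block labelled with an islet-mass range and holding its own difference, interval and p-value will be read as evidence about patients in that range. If the model has no treatment-by-IEQ/kg term, it cannot supply such evidence, because it contains one treatment effect per day for everyone. Three stratum rows would then look like three concordant results when they are one result printed three times, and a fourth time under Overall.

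Two features hide this. The per-arm least squares means still differ between strata, so the block looks like genuine stratum-level output. The interaction p-value, which would explain why the differences agree, is shown only when the term is kept. Islet mass is the trial's main prognostic factor (SAP 3.3 and 7.5.1), so this is where a reader would look for consistency of effect.

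**Working it through.** The plan states no figure for this table, so there is none to reproduce. The check is algebra, then one fitted example, then a frequency illustration.

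**1. Algebra.** Let T be treatment (0/1), t the visit (0 for Day 75, 1 for Day 365) and k the IEQ/kg stratum. The footnote model without the conditional terms is

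E(y) = mu + tau·T + delta·t + gamma_k + site + theta·T·t.

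Reparixin minus placebo in stratum k at visit t is tau + theta·t. It does not contain k. The estimate, SE, CI and p-value are therefore the same in every stratum and in Overall on that day. No assumption about the data is needed. Keeping treatment-by-site adds the same site average to every row, so the rows stay identical. Because theta is in the footnote model, Day 75 and Day 365 can differ from each other.

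With the interaction kept, the difference is tau + eta_k + theta·t, which is stratum-specific.

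**2. One simulated data set.** Inputs: N=100 (SAP 3.3), strata 34/42/24% (the 2006-2011 series in SAP 3.3) and 9 sites (the protocol amendment rationale). Assumed: between-patient SD 0.20, within-patient SD 0.12 IU/kg/day, true effects -0.15/-0.05/0. The interaction p-value was 0.54, so the rule drops the term. Day 75 results:

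| Stratum (IEQ/kg) | Term dropped: difference (95% CI), p | Term kept: difference (95% CI), p | t-test p |
|---|---|---|---|
| <2500 | -0.115 (-0.205 to -0.025), 0.012 | -0.162 (-0.311 to -0.013), 0.034 | 0.051 |
| 2500-5000 | -0.115 (-0.205 to -0.025), 0.012 | -0.114 (-0.242 to 0.014), 0.081 | 0.078 |
| >5000 | -0.115 (-0.205 to -0.025), 0.012 | -0.015 (-0.230 to 0.199), 0.889 | 0.937 |
| Overall | -0.115 (-0.205 to -0.025), 0.012 | -0.097 (-0.196 to 0.002), 0.055 | not computed |

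In the >5000 block the model row would show p=0.012 beside a t-test p of 0.937. At Day 365 all four dropped-term rows read -0.182, p=0.0001, against t-test p-values of 0.004, 0.043 and 0.273.

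**3. How often.** Assumed: N=100, strata 34/42/24%, SD 0.33, correlation between visits 0.7, no site effects. The SD is the midpoint of 0.32 and 0.34, the month-1 values in Protocol 2.4.2. The interaction was tested with 2 df at 0.10 on each patient's mean over the two visits. The p<0.05 event was counted on the day-specific rows that the table prints.

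| True effects (<2500 / 2500-5000 / >5000) | Term dropped | Dropped and >5000 row p<0.05, a given day | Same, both days |
|---|---|---|---|
| -0.25 / -0.10 / 0 | about 60% | about 29% | about 21% |
| -0.30 / 0 / 0 | about 36% | about 12% | about 7% |
| -0.10 / -0.05 / 0 | not tabulated here; see the range below | about 12% | about 6% |

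In the first case the common row targets about 0.34×(-0.25) + 0.42×(-0.10) + 0.24×0 = -0.127, against a true value of 0 above 5000 IEQ/kg. In the second it targets 0.34×(-0.30) = -0.102.

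Range for the drop rate: a separate run with 9 sites used between-patient SD 0.20 to 0.30 and within-patient SD 0.12. That implies a total SD of sqrt(0.04+0.0144)=0.23 to sqrt(0.09+0.0144)=0.32, and a correlation of 0.04/0.0544=0.74 to 0.09/0.1044=0.86. The term was dropped in about 91% of trials with no interaction, 82-87% with -0.10/-0.05/0, 59-74% with -0.20/-0.10/0 and 34-56% with -0.30/-0.15/0.

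**The case against.** The strongest reply is that little rests on these rows. Addendum 3.1 makes all of its efficacy endpoints exploratory. Section 3.2.2.2 asks only for summary statistics and t-tests by stratum, and both are in the table and sound. The footnote discloses the conditional term, so a careful reader can tell from the missing interaction row that it was dropped. If effects really are equal across strata, a common estimate is the right summary. All of this stands, and it confines the harm to reporting and interpretation. It does not remove the fault: the shell prints stratum-level model p-values, Addendum 3.1 leaves them without multiplicity correction, and nothing in the table labels them as pooled.

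The simulation inputs are also open to challenge. The SD comes from 6 and 3 islet allo-transplant patients at one month, and the effects and correlation are assumed. That is fair for the frequencies. The identity of the rows does not depend on them.

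Three stronger readings are not supported:

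- A reader might infer that the whole stratified table is invalid. Only the difference, SE, CI and p-value from the model are affected, and only when the interaction has p of 0.10 or more.
- A reader might infer that the sponsor offers the table as proof of benefit at every islet mass. No passage says so.
- A reader might infer that a treatment-by-IEQ/kg-by-time term is required. Without it, the Day 75 to Day 365 change in effect is the same in every stratum (theta; -0.067 in the example). That is a normal parsimony choice at this sample size, and Addendum 3.2.2.2 itself warns that the data may be too sparse for convergence.

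**Conclusion.** The point holds as a narrow defect in an exploratory table. Whenever treatment-by-IEQ/kg is dropped, the model-based difference, SE, CI and p-value are the same in all three strata and Overall on a given day. They can disagree with the adjacent t-test, and the interaction p-value is not displayed. This follows from the stated model alone.

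Dropping is likely with about 100 patients unless effects differ strongly between strata. Under the stated assumptions, a stratum with zero true effect prints p<0.05 through the pooled row in about 12% to 29% of trials on a given day. Calculating significance on the two-day mean would give about 33% to 34% in the -0.25/-0.10/0 case, but the table never prints that quantity. No primary or confirmatory conclusion is affected.

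**What to change.** Either of two changes to Addendum 3.2.2.2 and the Table 14.2.4.X shell and footnote is enough:

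1. Keep treatment-by-IEQ/kg, whatever its p-value, in the model that feeds the stratum rows. Always display its p-value. Take the Overall row from the model without the term, because in the example the kept-term Overall row weights the three strata equally and moves from -0.115 to -0.097.
2. Delete the model-based difference, CI and p-value rows from the stratum blocks, and rely there on the descriptive statistics and within-stratum t-tests.

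A three-way term with time is optional.

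Both are text and shell changes that need no new data, and the addendum is due to be finalised before database lock. Option 1 widens the stratum intervals. In the example the >5000 interval at Day 75 goes from a width of 0.179 to 0.429, about 2.4 times as wide. It also adds some sparsity or convergence risk, with about 24 patients expected in the smallest stratum. Option 2 has neither cost, but gives up covariate-adjusted stratum estimates.

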### 3.3 Exploratory Analysis

The safety population will be used for the summarization and analysis of all exploratory data.

#### 3.3.1 Inflammatory Chemokines/Cytokines

Inflammatory chemokines/cytokines to be summarized include serum levels of CXCL8, CCL2 (MCP-1), CCL3, CCL4, CXCL10 (IP-10), CXCL9 (MIG), IL-6, IL-10, INF- $\gamma$ , TNF- $\alpha$ , and IL-1 $\beta$ . Values are collected as 2 basal samples at pre-infusion hospital admission (6 to 24 hours apart) and at 6, 12, 24, 72, 120, and 168 hours after IAT. Mean values for each inflammatory chemokine/cytokine will be plotted for each sample time point by treatment group.

AUC0-72H will be computed as defined in Section 7.7.1 of SAP version 2.0. AUC0-72H for CCL2, IL-6 and IL-10 will be plotted versus IEQ as a regression curve for each treatment group. The slope and intercept of the regression line and R^2 will be calculated and displayed on the figure. The p-value testing the slope for difference from zero will also be displayed.

#### 3.3.2 MicroRNA-375

MicroRNA-375 (miR-375) is collected pre-transplant and at 6, 12, 24, 72, 120, and 168 hours post-transplant. Mean miR-375 values will be plotted for each sample time point by treatment group. AUC0-72H for miR-375 will be calculated as specified in section 2 and plotted versus IEQ as a regression curve for each treatment group. The slope and intercept of the regression line and R^2 will be calculated and displayed on the figure. The p-value testing the slope for difference from zero will also be displayed.

REP0112

Addendum to Statistical Analysis Plan

Figure 14.4.5.5	Area Under the Curve for C-peptide at Day 365 During First 4 Hours of a Mixed Meal Tolerance Test and Not Corrected for IEQ/kg Versus IEQ/kg – Only Patients Receiving IEQ/kg $\leq 5000$	Intent to Treat Population
Figure 14.4.5.6	Area Under the Curve for C-peptide at Day 365 During First 4 Hours of a Mixed Meal Tolerance Test and Not Corrected for IEQ/kg Versus IEQ/kg – Only Patients Receiving IEQ/kg $\leq 5000$	Per Protocol Population
Figure 14.4.11.1	Inflammatory Chemokines/ Cytokines, Plots of Mean Values Over Time	Safety Population
Figure 14.4.12.1	Area Under the Curve for CCL2, IL-6 and IL-10 During 72 Hours Following Transplant Versus IEQ, [Parameter Name]	Safety Population
Figure 14.4.15.1	miR-375, Plots of Mean Values over Time	Safety Population
Figure 14.4.15.2	Area Under the Curve for miR-375 During 72 Hours Following Transplant Versus IEQ	Safety Population

